Power	CHALO! 2.0 ($n_1=300$)	attention-matched control ($n_2=300$)	Digital coupon only ($n_2=300$)
>99%	0.5-0.75	0.2-0.5	0.15-0.45
>93%	0.5-0.6	0.35-0.45	0.35-0.45
>59%	0.5-0.6	0.4-0.5	0.4
>15%	0.5	0.45	0.45

*power is for CHALO! compared to each control separately

report HIV- testing, or condition,

13.2 Aim 1 sample size considerations: With a total of 1,000 participants, we expect at least 900 participants at 6 months, and 800 participants at 12 months. This will provide a total of 300 participants per arm at 6 months, and 266 participants per arm at 12 months. Based on findings from online intervention studies of HIV testing showing 1.7-2.2 increases in odds of testing in intervention vs. control conditions (across low and high income countries and heterogeneous online interventions),⁹⁷⁻¹⁰⁰ we estimate the proportion HIV testing at 6 months to be 70% for **CHALO! 2.0** ($n_1=300$) vs. 35% for attention-matched control ($n_2=300$) and 30% for digital coupon only ($n_2=300$). With the expected sample, the study's 2 main effects (**CHALO! 2.0** vs. attention-matched control and **CHALO! 2.0** vs. digital coupon only) have >99% power (Table 3). We also provide power estimates based on a wider range of parameters in Table 3, showing that we have sufficient power to detect between-group differences in the primary outcome with smaller effect sizes. Power was calculated using PASS software V15.0, with all analyses conducted with a two-tailed alpha of .025, resulting in a family-wise error rate of at most 0.05 for the primary outcome.

13.3 Aim 2 analyses: To test the hypothesis that **CHALO! 2.0** participants will be more likely to be linked to care (vs. controls), we will compare rates of linkage-to-prevention (i.e. counseling, PrEP-initiation) at 12 months among HIV-uninfected participants between study arms. As for Aim 1, we will perform 2-sample comparisons of proportions using chi-square tests, and will also perform logistic regression with linkage-to-prevention by 12 months as the outcome and study arm as the primary predictor, adjusting for covariates in Table 2 as required. We will repeat these analyses with linkage-to-care outcomes at 18 months, and with the outcome of self-reported linkage-to-prevention by 18 months. Additionally, using the entire study cohort, we will

Table 4. Proportion linked to HIV prevention by 12 months

Power	CHALO! 2.0 ($n_1=247$)	attention-matched control ($n_2=139$)	digital coupon only ($n_2=108$)

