>99%	0.15-0.4	0.05-0.1	0.03-0.01
>98%	0.3-0.4	0.1-0.2	0.03-0.01
>90%	0.3	0.15	0.1-0.15
>70%	0.2	0.1	0.08
>49%	0.3	0.2	0.2
>21%	0.15	0.1	0.1

*power is for CHALO! compared to each control separately

months, explore

whether participant factors and testing strategy predict HIV prevention (counseling or PrEP use) and treatment (ART initiation). For secondary and exploratory outcomes (defined in C7.1), we will repeat analyses as above, using ANOVA for or chi-square tests as appropriate.

13.4 Aim 2 sample size considerations: We anticipate that there will be no higher than 7% prevalence of undiagnosed HIV. Combined with expected HIV testing rates by 12 months of at least 75%, 45%, and 35% in the three arms, we anticipate the available sample size of HIV-uninfected participants for Aim 2 to be **CHALO! 2.0** ($n_1=247$), attention-matched control ($n_2=139$), and digital coupon ($n_2=108$). Based on HST's current linkage-to-care rates for HIV- negative individuals (30%),⁹⁰ we expect the rate of linkage-to-prevention care at 12 months to be 30% for **CHALO!** vs. 15% for attention-matched control vs. 5% for digital coupon only. The study's 2 main effects (**CHALO!** vs. Attention-matched control and **CHALO! 2.0** vs. digital coupon only) have >90% and >99% power, respectively (Table 4). We also provide power estimates for smaller effect sizes. The power was calculated using PASS software V15.0., with a two-tailed alpha of .025, resulting in a family-wise error rate of at most 0.05 for the primary outcome in the Aim 2. Due to an expected overall small number of individuals testing HIV- positive, we will not have power to detect potential differences between arms.

PROTECTION OF HUMAN SUBJECTS

A. RISKS TO HUMAN SUBJECTS

A1. HUMAN SUBJECTS INVOLVEMENT, CHARACTERISTICS, AND DESIGN.

A1a. Proposed human subject involvement. The protocol will include a 3-arm parallel, single blind, pragmatic randomized control trial of an online HIV digital messaging intervention (CHALO! 2.0) compared to an Attention-Matched Control, or a Digital Coupon only. Through online surveys, HIV testing utilization and results, and clinic visit data tracked by HST healthcare workers during the 12-week intervention period, and during the 15 months of follow-up, we will evaluate the outcomes for CHALO! 2.0.

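### At the printed Aim 2 sizes, the planned chi-square test has about 87-88% power against attention-matched control, not >90%, and three further rows of Table 4 are overstated in the same way

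*Combined protocol and SAP*

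**What the plan says.** For linkage-to-prevention at 12 months, section 13.3 states: "As for Aim 1, we will perform 2-sample comparisons of proportions using chi-square tests". Section 13.4 gives the inputs to the power calculation:

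- **Sizes:** 247 for CHALO! 2.0, 139 for attention-matched control and 108 for digital coupon only.
- **Rates:** "we expect the rate of linkage-to-prevention care at 12 months to be 30% for" CHALO!, and "15% for attention-matched control vs. 5% for digital coupon only".
- **Error rate:** "with a two-tailed alpha of .025, resulting in a family-wise error rate of at most 0.05".

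From these it concludes that the two main comparisons "have >90% and >99% power, respectively (Table 4"). The matching row of Table 4 reads ">90% 0.3 0.15 0.1-0.15": power, then the rates for CHALO! 2.0, attention-matched control and coupon only. The footnote says that power applies to each control separately. The software is named as PASS V15.0. The test statistic and the variance option are not named.

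**The concern.** The Pearson chi-square statistic for two proportions is the square of the z statistic with pooled variance. Power should therefore be computed with the pooled standard error in the critical value. When the arms are equal in size, pooled and unpooled formulas almost agree. Here the arms are unequal and the larger arm has the higher assumed rate. The unpooled standard error is then the smaller of the two, and a power figure based on it is too favourable for a chi-square test.

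The figure at issue is the headline power for the weaker of the two main comparisons on the Aim 2 primary outcome. Section 13.4 also offers the lower rows of Table 4 as evidence on smaller effects, so an overstatement there misleads a reader who uses them to judge what the trial can detect.

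**Working it through.** **Inputs** (section 13.4 and Table 4): n1 = 247, n2 = 139, p1 = 0.30, p2 = 0.15, two-sided alpha 0.025, so the critical value is z = 2.2414. The difference is d = 0.15.

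**Step 1. Reproduce the stated figure.** The unpooled standard error is

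SE_u = √(0.30 × 0.70/247 + 0.15 × 0.85/139) = 0.04204.

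Power = Φ(d/SE_u − z) = Φ(3.568 − 2.241) = Φ(1.327) = 90.8%. This agrees with >90%.

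**Step 2. Use the planned test.** The pooled rate is (247 × 0.30 + 139 × 0.15)/386 = 0.2460, and

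SE_p = √(0.2460 × 0.7540 × (1/247 + 1/139)) = 0.04566.

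Power = Φ((d − z × SE_p)/SE_u) = Φ((0.15 − 0.10234)/0.04204) = Φ(1.133) = 87.2%.

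Full enumeration of both binomial distributions, rejecting when the Pearson statistic exceeds z², gives 87.7%.

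**Step 3. Look for another route to >90%.** At the same inputs:

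| Method | Power |
|---|---|
| Arcsine formula | 88.3% |
| Unpooled formula, continuity-corrected | 88.4% |
| Pooled formula, continuity-corrected | 84.1% |
| Likelihood-ratio test, exact enumeration | 88.1% |
| Unpooled z-test, exact enumeration | 89.6% |

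None reaches 90%. The pooled formula exceeds 90% only at two-sided alpha 0.05 (92.5%), which is not the stated alpha.

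**Step 4. Repeat for the attention-matched rows that print a single pair of rates** (247 and 139, alpha 0.025):

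| Rates | Table 4 | Unpooled formula | Pooled formula | Exact chi-square |
|---|---|---|---|---|
| 30% / 15% | >90% | 90.8% | 87.2% | 87.7% |
| 20% / 10% | >70% | 70.4% | 63.1% | 64.3% |
| 30% / 20% | >49% | 49.8% | 45.8% | 47.0% |
| 15% / 10% | >21% | 21.9% | 18.6% | 18.8% |

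All four unpooled values lie just above the printed floor. All four chi-square values lie below it.

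**Step 5. Coupon only** (247 and 108). For 30% against 5%, power exceeds 99.9% by either formula. The other entries do not follow the pattern of step 4:

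| Rates | Table 4 | Unpooled formula | Pooled formula |
|---|---|---|---|
| 30% / 15% | >90% | 86.2% | 79.7% |
| 20% / 8% | >70% | 85.3% | 74.8% |
| 30% / 20% | >49% | 43.2% | 38.0% |
| 15% / 10% | >21% | 18.9% | 14.9% |

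The 20%/8% entry holds under both formulas; the other three hold under neither.

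**Step 6. Rows with ranges.** The >99% row prints 0.15-0.4 against 0.05-0.1, and the >98% row 0.3-0.4 against 0.1-0.2 (attention-matched), without pairings. Within the >99% row, 15%/5% fails under both formulas (88.0% unpooled, 79.8% pooled), while 30%/10% gives 99.5% under chi-square. Within the >98% row, 40%/20% gives 98.2% unpooled and 97.3% under chi-square, but 30%/10% clears the floor under either.

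**The case against.** Five points can be made on the other side.

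1. **The shortfall is small.** The headline moves by about 3 points, stays above 80%, and rests on round planning rates. This stands: it is a correction of a stated figure and not a failure of the design.

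2. **Part of the gap is approximation error.** Exact against exact, the unpooled test has 89.6% and the chi-square test 87.7%, a difference of about 1.8 points (0.8957 − 0.8774). This also stands, but it does not rescue the stated figure, because neither test reaches 90% when enumerated.

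3. **The cause is inferred.** The plan names the software but no variance option, so the unpooled formula is identified only because its numbers match. That is a fair limit on the explanation. The shortfall under the planned test does not depend on it.

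4. **A reader might infer that every Aim 2 power figure depends on the unpooled formula, or that the >99% and >98% rows are overstated for the same reason.** The documents do not support either reading. The coupon-only headline holds under both formulas, three coupon entries fail under both, and the two range rows cannot be tied to a test without assuming pairings that the plan does not give.

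5. **The printed sizes are themselves in doubt.** 247 is 266 × 0.93 and leaves out the 75% testing rate. 139 is 333 × 0.45 × 0.93 and 108 is 333 × 0.35 × 0.93; both start from all randomised participants and leave out 12-month attrition. Applying both factors gives 266 × 0.75 × 0.93 ≈ 186 and 266 × 0.45 × 0.93 ≈ 111, where chi-square power for 30% against 15% is about 77%. This separate matter is larger than the choice of variance. It makes any replacement figure conditional on the sizes, but it gives no support to >90%.

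**Conclusion.** The point holds for the attention-matched comparison. With 247 and 139 participants, rates of 30% and 15%, and two-sided alpha 0.025, the test named in section 13.3 has 87.2% power by formula and 87.7% exactly, so the type II error is about 12-13% where the plan implies less than 10%. In the three other single-pair rows the exact shortfall from the printed floor is about 6 points (20%/10%) and about 2 points each (30%/20% and 15%/10%).

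The conclusion rests on taking the printed sizes and rates as given and on reading chi-square as the uncorrected Pearson test; with a continuity correction, headline power would be lower, at 84.1%. It does not extend to the coupon-only headline, and it does not show that the trial is too small for Aim 2. Table 3 is barely touched: its arms are equal, and the two formulas differ there by less than half a point (for 50% against 40%, 59.2% and 58.8%).

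**What to change.** - Recompute section 13.4 and Table 4 for the Pearson chi-square test, and state the test and variance option used.
- Replace the >90% figure by about 87% at the printed sizes, or by the recomputed value if the Aim 2 sizes are revised. Settle the sizes first, so that the table is rerun only once.
- Correct the three other single-pair attention-matched rows: about 64% for 20%/10%, about 47% for 30%/20% and about 19% for 15%/10%.
- Print every row as an explicit pair of rates, with power given separately for each control. This also removes the ambiguity of the range rows and exposes the coupon entries that do not reach their row's floor.

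The cost is a rerun of the power program and new text, with a slightly less favourable headline. Enrolment, the planned test and alpha stay as they are.

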When participants present the coupons at any testing site, the tester-counselor (at HST sites) or lab technician (at the private lab sites) will enter the coupon code using an online coupon form. This system will register the coupon as being used, with time, date, and location of usage. Once test results are available, they will be entered in a manner specific to the testing site. At HST, the tester-counselor will enter test results directly into an Avegen HM form. If the coupon is used at the private lab, the data manager will retrieve results from the lab's secure online portal (along with the coupon use data) and enter it into the Avegen HM database. Two strategies will be used to capture testing data if a participant does not use the digital coupon provided by the trial. As described above, counselor-based testing that occurs at HST will be identified when the data manager cross-checks mobile phone numbers and emails for clients obtaining HIV tests against participant contact information. (At HST, contact information is provided by >99% of clients,⁹⁰ as required by Indian guidelines.⁹¹) Second, testing that occurs outside both HST and our private lab partner is expected to be rare, as subjects will receive free tests through the private lab (41 sites across Mumbai) or through HIV self-testing only if they use the digital coupon provided. Further, HST's 3 sites are the only MSM-specific free testing sites in Mumbai. In the very rare event that a participant does report testing elsewhere, this will be captured in the online survey, which will ask for the name and location and for the participant to upload a picture through secure link of their test completion result.

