This system will also alert study staff that a coupon was used with information about which coupon, so that study staff can follow-up with clients if needed about their results. If the coupon is used at HST, the tester/counselor will enter test results directly into a front-end HIV testing result form on Avegen HM (coupon-code and associated test result); if the coupon is used at a private lab, study staff will retrieve results from the lab's online portal, and then enter the test results into a front-end HIV testing result form on Avegen HM.

This approach has been generally used previously, including in a recent feasibility pilot by our private laboratory partner, and will enable real-time monitoring of test results, and accurate follow-up for clients.

Lab HIV testing data: Additionally, HST currently collects and verifies mobile phone numbers for clients coming in for testing to enable follow-up and linkage-to-care and as a requirement per Indian guidelines and requirements for testing. Subjects will only be able to receive the free test at the private lab or HIV self-test if they show the coupon. These steps will help ensure thorough assessment of our primary outcome and facilitate appropriate follow-up.

Linkage-to-care outcomes for HIV negative and positive individuals will be abstracted from HST's healthcare worker log, which contains information about linkage status and outcomes (HIV treatment registration, ART initiation, follow-up) or from HST's counseling and clinic utilization records which are housed on a computerized information system (CIS) at HST. Data from the HST healthcare worker log and the CIS can be linked to an individual's mobile phone number which will be how we match a participant's use of HST services. The data manager at HST on a monthly basis, will scan and match participant phone numbers to those in CIS; for any matches, that data will be extracted and merged into the Avegen HM database. The healthcare worker log also contains information about linkage/referrals to private HIV treatment clinics and for primary care/PrEP. Currently, HST refers clients interested in PrEP to two providers in Mumbai (vetted by HST to

provide MSM competent services). HST will also begin offering PrEP this summer to its patients, and will thus be available moving forward for all HST clients, including study participants.

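### Aim 2 linkage records are matched to participants by mobile number alone; adding keys the trial already holds would cheaply reduce missed linkages

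*Combined protocol and SAP*

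**What the plan says.** **Linkage.** Section A2, in the paragraph on linkage outcomes, takes counseling, PrEP and treatment linkage from the HST healthcare-worker log and the HST computerized information system (CIS). Both are tied to a participant through his mobile number: the data manager "will scan and match participant phone numbers to those in CIS". No second key is named. Section 8.3 likewise describes the CIS as linked to the client's mobile number.

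**HIV tests.** The main route is the digital coupon, whose number is linked to the study ID (sections 2.1, 8.2 and A2). For counselor-based tests at HST without a coupon, section 8.2 says the data manager "cross-checks mobile phone numbers and emails for clients obtaining HIV tests against participant contact information". Section 2.4 describes the same fallback with phone numbers only. Self-tests at HST and private-laboratory tests require the coupon.

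**Keys available.** Every participant gives and verifies both a WhatsApp number and an email address at enrolment (eligibility criterion 7; sections 6 and 6.2). Names are not requested (section B3a).

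**Power.** Section 13.4 says "we expect the rate of linkage-to-prevention care at 12 months to be 30% for" the intervention arm vs. "15% for attention-matched control vs. 5% for digital coupon only". It states that the two contrasts "have >90% and >99% power, respectively", "with a two-tailed alpha of .025, resulting in a family-wise error rate of at most 0.05". Section 13.3 gives the analysis: "we will perform 2-sample comparisons of proportions using chi-square tests".

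**The concern.** Section 13.4 builds the Aim 2 sample from expected testing rates and HIV-negative status, so a man enters the denominator through a test. The test is found by study ID or, for one fallback, by phone and possibly email. HST records enter the numerator by phone number alone. If HST holds a man under a different number from the one he enrolled with, he can stay in the denominator and be scored as not linked after receiving counseling or PrEP at HST.

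This can happen in two ways. A man may test with his coupon, perhaps at a private laboratory, and later be seen at HST under another number. Or he may test at HST without the coupon and be found by email under section 8.2, while the linkage match looks only at his phone. Contact details may also be updated at months 9 and 15 (sections 6.5 and A1c), and no section says whether old and new numbers are both searched.

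At stake is some under-counting of the Aim 2 primary outcome. Even when equal across arms, it shrinks the absolute difference and costs some power.

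**Working it through.** **Inputs (sections 13.3 and 13.4).** n = 247 (CHALO! 2.0), 139 (attention-matched control) and 108 (digital coupon only). Expected linkage is 30%, 15% and 5%. Two-sided alpha is 0.025, so z = 2.2414.

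**Reproducing the plan's figure.** The unpooled normal formula is

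power = Φ( (p1 − p2) / √[p1(1 − p1)/n1 + p2(1 − p2)/n2] − z ).

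- Against attention-matched control: 0.30 × 0.70/247 + 0.15 × 0.85/139 = 0.000850 + 0.000917 = 0.001767, whose square root is 0.04204. Then 0.15/0.04204 = 3.568, and 3.568 − 2.241 = 1.327, which gives 90.8%. The plan states more than 90%.
- Against digital coupon only: 0.25/0.03592 = 6.960, and 6.960 − 2.241 = 4.719, which gives more than 99.9%. The plan states more than 99%.
- The same formula matches other entries in the attention-control column of Table 4: 20% vs 10% gives 70.4% (stated >70%), 30% vs 20% gives 49.8% (>49%), and 15% vs 10% gives 21.9% (>21%).

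**Effect of missed linkages.** Let s be the share of linked men whom the match finds, equal in all arms, with no false matches. The observed rates become s × p1 and s × p2. Their ratio stays p1/p2. If p1 = p2 the observed rates are still equal, so type I error is unaffected. Only the difference shrinks, to s × (p1 − p2). The documents give no value of s, so the rows below are assumptions.

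| Missed | Observed rates | Difference | SE | Power, unpooled | Power, pooled |
|---|---|---|---|---|---|
| 0% | 30.0% vs 15.0% | 15.0 points | 4.204 points | 90.8% | 87.1% |
| 1% | 29.7% vs 14.85% | 14.85 points | 4.189 points | 90.4% | 86.7% |
| 2% | 29.4% vs 14.7% | 14.7 points | 4.174 points | 90.0% (just under) | 86.1% |
| 5% | 28.5% vs 14.25% | 14.25 points | 4.128 points | 88.7% | 84.5% |

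The pooled column uses the null variance of the chi-square test. It starts below 90% with no misses at all, so the choice of formula moves power by more (90.8 − 87.1 = 3.7 points) than a 5% miss does (90.8 − 88.7 = 2.1 points). Against digital coupon only, power stays above 99% in every row under either formula.

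**The case against.** The case for leaving this alone is strong in parts.

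- **Email has a small role for tests.** It appears in one sentence on one fallback, which section 2.4 describes by phone only. A reader might infer that the trial matches HIV tests by phone and email and linkage by phone. The documents do not support that: tests come mainly through the coupon. This stands. What remains is that the coupon carries a study ID and the stated linkage match does not use it.
- **Mismatches may be rare.** HST verifies the numbers of clients who come for testing, and section 8.2 says more than 99% of clients give contact information. That figure measures whether a contact was given, not whether it equals the enrolled number. Verification is described for testing clients, not for counseling or PrEP visits. Still, nothing in the documents points to a high mismatch rate.
- **Self-report is also a source.** Table 2 lists it beside the log and the clinic record. But the verification step in section 8.3 covers care outside HST and its partners, and section 13.3 treats self-reported linkage as a separate analysis. The documents do not say that self-report can fill a missed HST record in the primary outcome.
- **Email may not be on the record.** No section shows that counseling, PrEP or log entries hold an email, or that a man's services sit under the same client entry as his test. This stands, and it limits what the extra keys can recover.

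**Conclusion.** The stated linkage rule uses fewer keys than the trial holds, and it can miss linkages for men already counted as tested. This is a minor data-management point. With misses equal across arms, the contrast with attention-matched control loses 0.4 points of power at 1% missed, about 0.8 points at 2% and 2.1 points at 5%. The coupon-only contrast is not materially affected.

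These sizes rest on assumed miss rates, on misses being equal in all arms, and on the plan's own sample sizes and linkage rates. They are also an upper limit on the gain from the fix, because they credit it with recovering every miss.

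A reader might infer that phone-only matching seriously erodes Aim 2 power. The same formula gives 86.3% at 10% missed and 80.5% at 20%, but no figure in the documents supports rates of that order. A reader might also infer bias between arms. The documents give no reason to expect misses to differ by arm, and sections 7 and A1e blind the staff who collect these outcomes.

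**What to change.** State one matching rule and use it for both aims. Match log and CIS entries to a participant on any mobile number he has verified, on email where the HST record holds one, or on an HST client record already tied to his study ID through a test. Carry out the match blind to arm and report how many linkages each key found.

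In the same edit, bring sections 2.4 and 8.2 into line on the fallback for tests without a coupon, and say whether self-report can supply a missing HST record in the Aim 2 primary outcome. Reconcile the CIS cross-check interval as well, which is weekly in section 8.3 and monthly in section A2.

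The cost is extra keys in a merge the data manager already runs and a few more matches to review by hand. The gain is limited to records that carry one of these keys.
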